**Table 1. Assessments of physical function & mobility, nutrition, anxiety/depression, and health-related quality of life**

Domain	Measure	Details	When Collected
Screening Measures			
Medical History		A chart review will be conducted for every potential participant to assess eligibility (see criteria above) and to document surgery type.	Baseline (T1)

 The HGS test will only be administered when the assessment is conducted in person

Cognition		Participants must have a score of $\geq 20$ (< high school education) or $\geq 21$ (high school or more) on the MoCA or a score of $\geq 21$ on the SLUMS test and able to do ADLs to qualify for participation in this study. 	T1
Outcome Measures			
Demographics		Standard demographic information will be gathered via self-report and physical examination at baseline to describe the study sample.	T1
Physical Function & Mobility	5RSTS	The five repetition sit-to-stand test (5RSTS) is widely used as an indicator of lower limb strength among older adults.  The test is easy to administer and has good to high test-retest reliability.  In a meta-analysis conducted to generate normative values for this test, patients older than 60 years of age exceeding 11.4 sec were considered to have worse than average performance. 	T1, T2, T3, T4
	TMST	The two-minute step test (TMST) requires that individuals march in place as fast as possible for 2 minutes while lifting the knees to a height midway between their patella and iliac crest when standing. The performance on the test is defined as the number of right-side steps of the criterion height completed in 2 minutes. 	T1, T2, T3, T4
	HGS	Handgrip strength can be quantified by measuring the amount of static force that the hand can squeeze around a dynamometer. Low handgrip strength is a clinical marker of poor mobility and a better predictor of clinical outcomes than low muscle mass. Grip strength may also be used as a reliable surrogate for more complicated measures of muscle strength in the lower arms or legs.	T1, T2, T3, T4
Nutrition	Anthropometrics	Anthropometric measurements, including body mass index (BMI, weight in kilograms over the square of height in meters), mid-upper arm circumference, upper thigh circumference, waist circumference, hip circumference, and waist-to-hip ratio.	T1, T2, T3, T4
	PG-SGA	The PG-SGA includes assessments of weight, food intake, and nutrition impact symptoms.  The PG-SGA provides a global rating nutritional diagnosis (A, B, or C) and a continuous numerical score (1 to 30) for intervention triage. The Subjective Global Assessment (SGA), included in the PG-SGA, has also been applied and validated in predicting length of stay, postoperative complications, and mortality. 	T1, T2, T3, T4
	24-hour recall	Under the guidance of the Registered Dietitian Nutritionist, the study Physiologist will administer 24-hour dietary recalls once a week to assess compliance. This will be done using the USDA 5-step Multiple Pass Method (Conway et al 2003) to capture detailed information about all foods and beverages consumed by the participant in the past 24 hours. The USDA multiple-pass method for dietary recall consists of five steps: (a) the quick list, which is an uninterrupted listing by the subject of foods and beverages consumed; (b) the forgotten foods list, which queries the subject on categories of foods that have been documented as frequently forgotten; (c) a time and occasion at which foods were consumed; (d) the detail cycle, which elicits descriptions of foods and amounts eaten aided by the interactive use of the USDA	Weekly phone calls

		
Food Model Booklet and measuring guides; and finally (e) the final probe review.
 
The USDA Food Model Booklet (9) was used to assist in portion-size estimation of consumed foods. It has eight sections: (a) the forgotten foods list, (b) glasses and mugs, (c) bowls, (d) mounds, (e) circles, (f) grid and thickness blocks, (g) wedges, and (h) shapes and chicken pieces.
	
Health-related Quality of Life	SF-36	
The 36-Item Short-Form Health Survey (SF-36) contains 36 items that are scored as 8 multi-item scales, namely vitality, physical functioning, bodily pain, general health perceptions, physical role functioning, emotional role functioning, social role functioning, and mental health.
	T1, T4, T5
Anxiety and Depression	HADS	
Hospital Anxiety and Depression Scale (HADS) is a questionnaire involving statements relevant to generalized anxiety and depression. Each item is answered on a four-point (0–3) response category, and the possible scores range from 0 to 21 for anxiety and 0 to 21 for depression.
	T1, T2, T3, T4, T5

## 9.0 Adverse Events

Because the intervention closely resembles daily activities and is so closely monitored, we expect a low rate of adverse events. All adverse events will be reported per Durham VAMC requirements. All Serious, Unanticipated and Related Adverse Events will be reported to IRB within five business days of a member of the study team learning of the event. All other adverse events will be reported at the time of continuing review. Should any incident such as theft or loss of data, unauthorized access of sensitive data, or non-compliance with security controls occur, it will be immediately reported according to VA policy. All incidents regarding information security/privacy incidents will be reported to the ISO and PO within one hour of report.

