## **12.0 Withdrawal of Participants**

Participants will be withdrawn from the study if any of the following occur:

- Withdrawal of study consent
- Inability to continue with the exercise or nutritional support program for any reason
- At the Principal Investigator's discretion

If a participant is withdrawn, follow-up for the purposes of research is not anticipated. The subject will continue to see their respective health care providers during scheduled clinic visits.

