## **13.0 Data Analysis and Statistical Considerations**

Feasibility will be assessed by calculating the acceptance rate, measured as the number of patients enrolled divided by the number eligible. In addition, we will evaluate veterans' reasons for enrollment or non-enrollment in the program using patient interviews and semi-structured questionnaire (see Appendix 4). No PHI will be recorded in questionnaires obtained from eligible but non-recruited veterans.

Acceptability will be measured by rate of compliance with the exercise/nutrition programs. For the exercise intervention, the percentage of patients completing  $\geq 75\%$  of sessions divided by the number of enrolled patients will be calculated. For the nutritional intervention, compliance will be measured by the percentage of patients with  $\geq 75\%$  adherence to protein intake goal, as assessed using the text message-based nutrition diary, lids returned, and 24-hour recall administered during the weekly telephone call.

Safety will be evaluated by the number of adverse events (significant injury or medical event) during exercise. A significant injury or medical event is defined as an event that causes the participant to seek attention from a health professional or limits their activities of daily living for at least two days.

Effect size will be estimated by comparing physical function before and after the prehabilitation intervention, as measured by the 5RSTS and the 2-minute step tests using Cohen's D. Changes in health-related quality of life (SF-36) and anxiety and depression (HADS) before surgery and at the 6-week and 24-week study periods following surgery will be calculated.

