#### **Appendix 5: For dropouts:**

1. Why did you stop participating in this program?
  - a. I don't see the utility of this
  - b. The exercise routine is too hard
  - c. The exercise routine is boring
  - d. I don't like the trainer
  - e. I don't like the nutritional supplements
  - f. I don't like the text messages and/or phone calls
  - g. I can't figure out how to use the device
  - h. I don't have the time
  - i. Other
2. How many sessions did you participate in?

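### An exercise injury that ends participation may never be classified for the Section 13 safety count, because Section 12 plans no research follow-up after withdrawal

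*Combined protocol and SAP*

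**What the plan says.** Safety belongs to the first specific aim and to the central hypothesis (Section 3.0). Section 13.0 gives its one measure: "Safety will be evaluated by the number of adverse events (significant injury or medical event) during exercise". An event is significant if it leads the participant to "seek attention from a health professional or limits their activities of daily living for at least two days". The two criteria are alternatives, so either one is enough.

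Section 12.0 lists the grounds for withdrawal, among them "Inability to continue with the exercise or nutritional support program for any reason". It continues: "If a participant is withdrawn, follow-up for the purposes of research is not anticipated". It leaves the participant to routine clinic visits and makes no exception for an adverse event that is still open.

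Section 9.0 covers reporting. It says "All adverse events will be reported per Durham VAMC requirements", then "All Serious, Unanticipated and Related Adverse Events will be reported to IRB within five business days of a member of the study team learning" about it, and "All other adverse events will be reported at the time of continuing review". These sentences set when known events are reported. They do not say how the Section 13 criteria are established.

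Appendix 5, the form for dropouts, asks "Why did you stop participating in this program" and offers eight specific reasons plus 'Other'. None of the eight is injury or a medical problem.

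**The concern.** The event being counted can itself trigger the rule that ends research contact. A participant hurt during exercise who cannot go on is withdrawn under Section 12. Whether that injury counts under Section 13 may depend on the following days: whether the participant saw a professional, and whether daily activities were still restricted two days later. The plan does not say that anyone will ask.

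Any such loss would not be random. It falls on participants whose injury was bad enough to stop the program, so leaving unclassified injuries out makes the program look safer than it was. The study has 24 patients and is meant to inform a larger multicenter trial (Section 2.0). Reporting no events and reporting one event are different messages to carry into that trial.

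**Working it through.** The plan states no event rate, safety threshold or interval, so it has no figure to reproduce. The check is a reading of the rules together, followed by a calculation for scale.

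**Tracing one injury through the text**

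1. A participant is injured while exercising. Supervised sessions take place three days a week (Section 8.2.1). Daily texts prompt independent exercise between them (Section 8.2.3), and Appendix 2 asks participants to raise their daily step counts. Staff therefore see some of the exercise, but not all of it. Section 13 does not restrict the count to supervised sessions.
2. The participant cannot continue and is withdrawn (Section 12).
3. Classification under Section 13 needs two facts. Whether care was sought may be known at once or only later. Whether activities were limited for two days cannot be known on the day of the event.
4. After withdrawal, Section 12 anticipates no research contact. Weekly calls and texts support the program (Section 8.2.3), and nothing says they continue for someone who has left it.
5. Other sources might supply the facts: the medical record (Sections 14.1 and 14.2), the adverse events log (Section 14.4.1) and the dropout form. None is tied to the two criteria. Care outside the VA, or two restricted days at home, may appear in none of them.

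**Scale**

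Input: n = 24 (Section 5.1). Event counts are assumed. The exact (Clopper-Pearson) 95% interval for x events runs from the 2.5% quantile of Beta(x, n − x + 1) to the 97.5% quantile of Beta(x + 1, n − x). For x = 0 the lower limit is 0 and the upper limit is 1 − 0.025^(1/24) = 0.142.

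| Participants with an event | Proportion | Exact 95% CI |
|---|---|---|
| 0/24 | 0% | 0% to 14.2% |
| 1/24 | 4.2% | 0.1% to 21.1% |
| 2/24 | 8.3% | 1.0% to 27.0% |

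If no events are recorded and w injured participants leave unclassified, the true proportion lies between 0 and w/24. The upper bound is 4.2% for w = 1, 8.3% for w = 2 and 16.7% for w = 4.

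**How often**

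Let q be the chance that a participant has an injury that truly meets Section 13, ends participation and is left unclassified. The documents give no basis for q. The expected undercount is 24q, and the chance of at least one miss is 1 − (1 − q)^24.

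| Assumed q | Expected undercount | Chance of at least one miss |
|---|---|---|
| 1% | 0.24 | 0.21 |
| 2% | 0.48 | 0.38 |
| 5% | 1.2 | 0.71 |

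These values show sensitivity only; they are not estimates.

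**The case against.** **The gap is narrow in practice.** Contact is frequent, so inability to continue may become clear only at the next session, about when the two-day criterion can be judged. The duty in Section 9 covers all adverse events, with no exception for later withdrawal. Section 11 says missing information will be resolved or reported. Chart review would show VA care, 'Other' can hold an injury, and *not anticipated* does not forbid a call. An injury that stops even seated exercise would often limit daily activities or prompt care, so the withdrawal itself is informative. All of this stands, and it limits how many events would be lost. It does not close the gap, because no provision directs anyone to establish the two criteria after withdrawal, and the one explicit sentence on follow-up points the other way.

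**No stated decision depends on the shift.** Section 13 plans a number of events, without a proportion, interval or threshold. This is correct, and the intervals above are for illustration. The count is still the only safety result planned for Aim 1.

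**Stronger readings that the documents do not support.**

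- *Serious injuries would go uncounted.* A serious injury would usually involve professional care and so qualify without follow-up.
- *IRB reporting is too slow.* A reader might note that the five-day rule requires events to be serious, unanticipated and related together, and that Section 4.1 calls physical injury inherent in exercise programs. From this the reader might infer that a serious related injury waits for continuing review. Section 9 also applies Durham VAMC requirements, which are not in the documents and may be stricter, and such an injury could be judged unanticipated in its severity. No defect in reporting time can be shown.
- *Those most likely to have a countable event are those most likely to be withdrawn.* Any resulting visit to a professional is enough for Section 13, while Section 12 requires inability to continue. Many countable events need not end participation.

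**Conclusion.** The point holds in a limited form. Followed as written, Sections 12 and 13 together can leave an injury that ends participation unclassified. The exposed cases are mainly milder injuries, those with delayed or non-VA care, and those arising in unsupervised exercise. The resulting bias in the safety count is downward, provided that unclassified injuries are left out of it; the plan does not say how they are handled.

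One miss would change the result from 1/24 (4.2%, 95% CI 0.1% to 21.1%) to 0/24 (0% to 14.2%). Whether any miss would occur cannot be judged from the documents. The change is worth making because it is cheap and makes the Aim 1 safety count more complete. The point is no evidence that the program is unsafe, and it does not call for a change to the reporting rule in Section 9.

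**What to change.** Amend Section 12: when an injury or medical event leads to withdrawal and consent has not been withdrawn, the team makes one telephone call at least two days after the event. The call establishes both Section 13 criteria (whether professional care was sought, and whether daily activities were limited for two days or more), and the answers go into the existing adverse events log. Add 'injury or medical problem' as an answer in Appendix 5.

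The cost is a short amendment and one call per withdrawal of this kind, with no new staff or committee. The consent form, which is not among the documents, may need a line allowing the call. The call cannot be made once consent is withdrawn, so those cases should be reported as unclassified.

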## 10.0 Costs and/or Payments to Subjects

Participants will be reimbursed \$50 for each in-person clinic visit they make for purposes of study procedures (range \$100-\$200). The initial preoperative visit and the 6-week postoperative visit for all participants with an optional second preop visit immediately prior to surgery if the T2 assessment cannot be performed on the day of surgery and at T5 if the assessments cannot be performed over the telephone.

## 11.0 Data and Safety Monitoring

Hardcopy documents, including those containing PHI, will be stored in folders and binders and kept inside a locked cabinet in the Anesthesia Research Office (C3011A), and are accessible to research personnel only. Electronic data will be stored on secure VA servers accessible only to study personnel [S:\Anesthesia Research\[name]\PREVENT\Data]. Study data will be reviewed as patients are enrolled and any member of the study team may review source documents or data at any time. Protocol deviations, data discrepancies, errors, or missing information will be resolved and/or reported per DVAHCS and IRB policy.

## **12.0 Withdrawal of Participants**

Participants will be withdrawn from the study if any of the following occur:

- Withdrawal of study consent
- Inability to continue with the exercise or nutritional support program for any reason
- At the Principal Investigator's discretion

If a participant is withdrawn, follow-up for the purposes of research is not anticipated. The subject will continue to see their respective health care providers during scheduled clinic visits.

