### **8.2.3 Assessments and Supplemental Interventions**

Objective physical function assessments will be performed at baseline (T1), before surgery (T2), immediately prior to hospital discharge (T3), and then again 6 weeks postoperatively (T4) by administering the **2MST,5RSTS and HGS tests** either in-person or remotely using telehealth technology (see Table 1 for details).

The nutritional support intervention will be assessed at baseline (T1), before surgery (T2), immediately prior to hospital discharge (T3) and then again 6 weeks postoperatively (T4) using **anthropometrics**, a weekly **24-hour dietary recall** (via telephone or videoconference, see Appendix 6), and the administration of the **PG-GSA**, a validated nutritional assessment instrument (see Table 1 for details).

Both the exercise and nutritional support programs will be supplemented with **text messages** on veterans who own text message-enabled cellphones.

Messages will be sent daily using the VA Annie App during the prehabilitation period (T1 - T2). The purpose of these messages is as a reminder about the timing of training sessions, to prompt independent exercise on days between formal sessions, to take protein supplement following exercise, and to maintain a nutritional diary (see above).

Text messages and weekly telephone or videoconference calls will resume upon hospital discharge and extend until the 6-week follow-up visit (T4).

Anxiety, depression, and health-related quality of life will be assessed using the HADS and SF-36 questionnaires at baseline (T1), before surgery (T2), immediately prior to hospital discharge (T3), and 6 and 24 weeks postoperatively (T4 and T5, respectively). These questionnaires will be administered either in person or via telephone or videoconference.

Details and timelines for each of these assessment instruments are described in Table 1.

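### Section 12 makes inability to continue the program a ground for leaving the study, with no research follow-up expected. Section 13 has no Aim 2 analysis set or missing-outcome rule, so effect sizes will tend to describe only those who could continue.

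*Combined protocol and SAP*

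**What the plan says.** Section 12.0 gives three grounds for withdrawing a participant from the study: withdrawn consent, the Principal Investigator's discretion, and "Inability to continue with the exercise or nutritional support program for any reason". It continues: "If a participant is withdrawn, follow-up for the purposes of research is not anticipated". Being unable to continue either component is enough, even in someone still willing to be assessed.

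For Aim 2, Section 13.0 says: "Effect size will be estimated by comparing physical function before and after the prehabilitation intervention". The measures named there are the five-repetition sit-to-stand and the two-minute step test, and the statistic is Cohen's D. For the questionnaires it plans "Changes in health-related quality of life (SF-36) and anxiety and depression (HADS) before surgery and at the 6-week and 24-week study periods following surgery". Neither sentence says who is analysed or what happens when a value is missing. The one denominator fixed at all enrolled belongs to exercise compliance under Aim 1: "sessions divided by the number of enrolled patients will be calculated".

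Section 3.0 plans a single cohort of 24, expects Cohen's effects of about 1.6 for functional capacity and 0.4 for quality of life, and refers to attrition without giving a rate. Section 2.0 says the findings should inform the design of a larger multicenter trial. Section 8.2.3 allows the questionnaires by telephone or video and the function tests by telehealth; the footnote to Table 1 restricts handgrip to in-person visits.

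**The concern.** Stopping an intervention and leaving a study are different events, and Section 12.0 treats the first as a cause of the second. The people affected are unlikely to be a random subset: this is a frail cohort facing high-risk surgery, and those who cannot keep up the program may well be those whose function or quality of life improves least. If their outcomes are not collected, the before/after estimates answer a narrower question (change among those able to continue) than the one Aim 2 appears to ask (change among veterans offered the program).

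The stake is the use of these estimates in planning the multicenter trial. A larger sample would not remove this kind of bias, and outcomes that were never collected cannot be recovered later.

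**Working it through.** **Step 1: what is lost, and when.** The function effect size compares values before and after prehabilitation, so it needs T1 and T2.
- *Stops before T2:* no T2 sit-to-stand or step-test value, and no later SF-36 or HADS values.
- *Stops after T2:* the T1 to T2 function comparison survives, but the remaining SF-36 and HADS values are lost. The 24-week questionnaires (T5) are among them, although they fall well after the 6-week postoperative program ends.

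**Step 2: does anything elsewhere repair this?** Section 11.0 mentions missing information, but as a matter of resolving and reporting data problems, not as an analysis rule. Appendix 5 asks dropouts why they stopped and how many sessions they attended; it collects no outcomes.

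**Step 3: what is not affected.** The acceptance rate is enrolled over eligible. Exercise acceptability divides by all enrolled. Safety is a count of events during exercise.

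**Step 4: an illustration of size.** The plan has no figure of its own to reproduce, since 24 rests on feasibility. From Section 3.0: N = 24, D = 1.6 for function and D = 0.4 for quality of life. My assumptions:
- D is the effect in those who continue, whose changes have SD 1.
- A share p of those enrolled stops. For function, only stopping before T2 counts.
- The mean change in those who stop is m.

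Mean over all enrolled = (1 − p)D + pm.

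Take 5 of 24, so p = 0.2083, with m = 0. The mean is 0.7917 × 1.6 = 1.267 for function and 0.7917 × 0.4 = 0.317 for quality of life. Section 13.0 does not name the SD that standardises Cohen's D, so three readings are shown:

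| Standardising SD | Variance, D = 1.6 | d, function | Variance, D = 0.4 | d, quality of life |
|---|---|---|---|---|
| Fixed at 1 (for example baseline) | 1 | 1.27 | 1 | 0.32 |
| SD of change, stoppers all exactly 0: (1 − p) + p(1 − p)D² | 0.792 + 0.422 = 1.214 | 1.267/1.102 = 1.15 | 0.792 + 0.026 = 0.818 | 0.317/0.904 = 0.35 |
| SD of change, stoppers vary around 0 with SD 1: 1 + p(1 − p)D² | 1.422 | 1.267/1.193 = 1.06 | 1.026 | 0.317/1.013 = 0.31 |

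**Step 5: range over the assumptions.** On the last row's scale, 2 of 24 stopping gives 1.34 and 0.36, and 7 of 24 gives 0.92 and 0.28. If those who stop instead decline by half an SD (m = −0.5, SD 1), the variance is 1 + p(1 − p)(D − m)². With 5 of 24:
- Function: mean 1.267 − 0.104 = 1.163, variance 1 + 0.1649 × 4.41 = 1.727, d = 1.163/1.314 = 0.88.
- Quality of life: mean 0.317 − 0.104 = 0.213, variance 1 + 0.1649 × 0.81 = 1.134, d = 0.213/1.065 = 0.20.

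**The case against.** The best defence is that this is an exploratory pilot of 24 people with an uncontrolled before/after estimate. Attrition is only one of its limits, and the main Aim 1 measures are intact. Saying that follow-up is not anticipated is also softer than forbidding it. Some who cannot exercise will be unable to do a sit-to-stand or step test, so few function values may be recovered. All of this stands, and it limits the weight of the point. It does not remove it: no follow-up is still the default, nothing else in the plan provides for these outcomes, and a questionnaire by telephone does not depend on being able to exercise.

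Three stronger readings are tempting, and the documents support none of them.
- *The effect sizes are known to be inflated, by a known amount.* No withdrawal rate and no outcome for those who stop is given. The 16 to 100% range in Section 2.0 is compliance, not withdrawal.
- *Aim 2 is a per-protocol analysis that discards data.* Nothing says values collected before withdrawal are dropped, and a participant with low adherence who can continue stays in.
- *The feasibility and safety results are compromised.* The measures listed in Step 3 do not depend on follow-up after withdrawal.

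**Conclusion.** The point holds as a design weakness worth correcting, not as an error in any stated figure. Section 12.0 merges stopping the program with leaving the study, and Section 13.0 supplies no analysis set or missing-outcome rule for Aim 2, so the estimates will tend to describe those who could continue. An overstatement for all enrolled veterans is plausible but unproven, and its size cannot be derived from the documents.

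The illustrative shifts, from 1.6 to about 1.06–1.27 and from 0.4 to about 0.31–0.35, rest on an assumed 5 of 24 stopping (before T2, for function), no mean change in them, and the Section 3.0 effects holding in those who continue. Fewer stoppers would shrink the shift; more of them, or a decline among them, would enlarge it.

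Two neighbouring defects are separate, because they would exist with no withdrawals at all. Section 13.0 does not name the SD for Cohen's D. Section 8.2.3 schedules the SF-36 at T1 to T5, while Table 1 lists T1, T4 and T5 only; those two passages must be reconciled.

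**What to change.** **Section 12.0.** Distinguish stopping the exercise or nutrition program from leaving the study, without changing when anyone stops the program. Unless consent is withdrawn or the investigator documents a reason to end follow-up, keep the scheduled T2 to T5 assessments where the participant is able. Use the remote options already in Section 8.2.3 (not for handgrip). Otherwise record that the participant was unable, and why.

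**Section 13.0.** State that Aim 2 includes all enrolled participants with data, whatever number of sessions they completed. Report the number observed at each time point and the number and timing of discontinuations. Because that set still omits people without values, add a sensitivity analysis for missing outcomes at T2, T4 and T5, covering both no change and a worse-than-no-change scenario for those who stopped. Say what spread is assigned: giving everyone exactly zero shrinks the SD of change and shows less of the shift (1.15 against 1.06 above).

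**Cost.** A wording amendment, possibly with IRB review, and a few extra remote contacts by existing staff. Some who stop will still be unable to do the physical tests, and the resulting estimate may be less favourable.
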